5.3.2 Safety evaluation

Observation purpose: To evaluate the safety of the pre-filled flush syringe for flushing and/or locking the end of catheter line.

(1) Safety

> Adverse events and serious adverse events

(2) Method and time selection for evaluating, recording and analyzing safety indicators

1) Evaluation method (calculation formula)

• Calculate the incidence of adverse events, serious adverse events: number of subjects experiencing the above events/total number of subjects \times 100%.

2) Time selection

Adverse events/serious adverse events are recorded at all times.

3) Analytical method

See section 6.4 for statistical analysis method.

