12.1.3 Correlation of adverse event with devices

Five criteria that investigators will use for judging the relationship between adverse events and study devices. Among them, "definitely related, probably related, and possibly related" will be determined to be adverse events related to the study devices.

(1) Definitely related: It conforms to the known reaction type of the device used, conforms to a reasonable time sequence after treatment, the adverse event cannot be explained by other reasons, the adverse event is alleviated or disappear after the treatment is stopped, the adverse event reappears after reuse, and the adverse event cannot be explained by the subject's current disease;

(2) Probably related: It conforms to the known reaction type of the device used, conforms to a reasonable time sequence after treatment, the adverse event cannot be explained by other reasons, the adverse event is alleviated or disappear after the treatment is stopped, and it is impossible to judge whether the adverse event will occur again after reuse, the adverse event cannot be explained by the subject's current disease;

(3) Possibly related: It conforms to the known reaction type of the device used, conforms to a reasonable time sequence after treatment, the adverse event cannot be explained by other reasons, the adverse event may be alleviated or disappear after treatment is stopped, and it is impossible to judge whether the adverse event will occur again after reuse, the adverse event can be explained by the subject's current disease;

(4) Possibly unrelated: It conforms to the known reaction type of the device used, conforms to a reasonable time sequence after treatment, the adverse event can be explained by other reasons, the adverse event may be alleviated or disappear after treatment is stopped, and it is impossible to judge whether the adverse event will occur again after reuse, the adverse event can be explained by the subject's current disease;

(5) Unrelated: It does not conform to the known reaction type of the device used, does not conform to a reasonable time sequence after treatment, the adverse event can be explained by other reasons, the adverse event does not alleviate or disappear after treatment is stopped, and the adverse event does not occur again after reuse, adverse events can be explained by the subject's current disease.

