12.1.4 Observation and recording of adverse events

The investigator shall collect and record the adverse events from each subject during the period from the signing of informed consent form to the termination of follow-up. Any adverse event, regardless of its severity, or whether it is related to the medical device, is required to be recorded and described on the adverse event form for study medical records. Investigators need to determine the date of occurrence, severity, whether to take corresponding measures, and to judge the correlation between the adverse events and the medical devices.

The subject undergoing such adverse events shall be followed up until the adverse events are recovered (return to normal state or to baseline state), or until the condition is stable, or until a reasonable explanation is available.

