4.1.2 Secondary effectiveness indicators

Ease of pushing of the plunger during catheter flushing and/or locking

Definition: The pushability of the plunger when the pre-filled flush syringe is flushing and/or locking.

Observation time: At the time of implementation and completion of catheter flushing and/or locking.

Evaluation criteria: Ease of pushing of the plunger during catheter flushing and/or locking = (number of cases whose score ≥ 3 /total number of cases evaluated) $\times 100\%$.

Evaluation method:

As assessed by a nurse, who is asked to answer the following questions:

Whether it is easy to push the plunger (ease of pushing) during catheter flushing and/or locking?

5-score scale:

- 5 scores: Very easy;
- 3 scores: Easy;
- 1 score: Difficult.
- 4.2 Safety indicators
- Adverse events and serious adverse events.

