6.4 Safety evaluation

(1) Evaluation Indicators

Adverse events and serious adverse events

(2) Evaluation method

Safety analysis is conducted based on safety set (SS).

The Medical Dictionary For Regulatory Activities (MedDRA) version 25.1 is used for adverse event coding. Adverse events that occur prior to the start of the flush syringe treatment are only shown in the list.

Adverse events that occur not earlier than the use of investigational device or that exist before the use of investigational device but get severe at or after the use of the investigational device are considered TEAEs. If multiple adverse events of the same preferred term (PT) occur in the same subject, the most serious one is used for the final intergroup comparison.

The number, frequency and proportion of TEAEs and investigational device-related TEAEs occurring in each group are tabulated and summarized according to system organ classification (SOC), preferred term (PT) and severity. If the same adverse event occurs multiple times in the same subject, the most serious one is used for analysis.

Severe TEAEs, TEAEs leading to study discontinuation, and TEAEs leading to death are summarized for each group by system organ classification (SOC) and preferred term (PT), respectively.

Adverse events related to the investigational device include those judged as "definitely related, likely related, and probably related" in relation to the investigational device.

Adverse events leading to study discontinuation (including whether the adverse event leads to withdrawal from the trial) are judged as "yes".

Adverse events leading to death (including prognosis) are selected as "Death".

All adverse events during the study are detailed in the list.

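### SAP 6.4's device-related labels do not match the protocol's causality scale, and its 'Severe TEAEs' summary leaves the reporting of serious events ambiguous

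*SAP*

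**What the plan says.** On causality, protocol 12.1.3 gives five grades: definitely, probably and possibly related, possibly unrelated, and unrelated. It then fixes the cut: "Among them, 'definitely related, probably related, and possibly related' will be determined to be adverse events related to the study devices". SAP 6.4 sets its own: "Adverse events related to the investigational device include those judged as 'definitely related, likely related, and probably related". That rule feeds the device-related TEAE table, which is broken down by SOC, PT and severity.

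On serious events, SAP 4.2 gives the safety indicators as "Adverse events and serious adverse events", and the first part of SAP 6.4 repeats them. The method part then covers all TEAEs and device-related TEAEs, and adds: "Severe TEAEs, TEAEs leading to study discontinuation, and TEAEs leading to death are summarized for each group". It names no summary of serious events. Protocol 5.3.2 is explicit that there should be one: "Calculate the incidence of adverse events, serious adverse events: number of subjects experiencing the above events/total number of subjects".

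On the time window, protocol 12.1.4 collects adverse events "during the period from the signing of informed consent form to the termination of follow-up", whereas SAP 6.4 tabulates treatment-emergent events and says of earlier ones: "Adverse events that occur prior to the start of the flush syringe treatment are only shown in the list".

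**The concern.** The SAP list is an operative rule: someone has to turn it into a filter on a recorded causality grade. If the data carry the protocol's grades and the filter carries the SAP's labels, one of the three grades that the protocol calls related matches nothing, and those events leave the table.

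That grade may matter in this design (an inference from the definitions in protocol 12.1.3, not from data). 'Definitely' requires the event to return on reuse, but the flow chart has one flush-treatment visit. 'Probably' requires that the subject's current disease cannot explain the event, but every subject is an inpatient. 'Possibly' is the only related grade that allows an explanation by current disease.

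For serious events, the question is whether the SAP specifies the SAE incidence that the protocol defines. Severity (protocol 12.1.2) and seriousness (protocol 12.3) are separate definitions, so a table of one cannot stand in for the other.

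**Working it through.** The plan states no figure to reproduce. The check is a comparison of the texts.

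**1. Causality labels**

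| Protocol 12.1.3 grade | Related per protocol | SAP rule read literally | SAP rule read as a shifted translation |
|---|---|---|---|
| Definitely related | yes | yes | yes |
| Probably related | yes | yes | yes (as SAP 'likely') |
| Possibly related | yes | **no** | yes (as SAP 'probably') |
| Possibly unrelated | no | no | no |
| Unrelated | no | no | no |

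Two of the SAP's three labels are on the protocol scale and one ('likely') is not. On the literal reading, one of the protocol's three related grades is left out. On the translation reading, none is.

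**2. 'Severe' and 'serious' in the SAP**

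- Table 3.1 (SAP 3.4) writes 'severe' in the adverse-event row where the protocol flow chart writes 'serious'. This favours 'Severe TEAEs' meaning serious TEAEs.
- SAP 6.4 already tabulates TEAEs by severity, so a separate severe-grade summary would largely repeat that table. This favours the same reading.
- The repeated-event rule in SAP 6.4 runs the other way, using 'serious' where the grade appears to be meant: "If the same adverse event occurs multiple times in the same subject, the most serious one is used for analysis".
- The TEAE definition in SAP 6.4 uses 'severe' for worsening, and SAP 7.2 uses it for the grade. This favours the grade reading.
- SAP 6.5 uses 'serious' correctly for SAEs, but only for those caused by device deficiencies.

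The usage is inconsistent in both directions, and the text alone does not decide it.

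**3. Why the two readings differ**

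The severe grade in protocol 12.1.2 concerns danger to life, death or disability. Protocol 12.3 also makes an event serious if it prolongs hospitalization, so such an event can be serious without being graded severe. Conversely, SAP 7.2 fills a missing grade after the start of treatment with 'severe', so a severe-grade table can include events that are not serious.

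**4. Window**

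Protocol 5.3.2 places no treatment-emergent limit on SAE incidence, and collection runs from consent, with screening of up to 3 days. A serious-TEAE rate alone would therefore not be the protocol's quantity. Nor can every event before device use be given to a group, because a consented subject who is never randomized has none.

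**5. Scale**

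No event counts are given. Planned size is 378/2 = 189 per group, so one subject moves a group rate by 1/189 = 0.53 percentage points. If the planned 10% drop-out all left the SS (an assumption), 189 × 0.9 = 170.1, about 170 per group, and 1/170 = 0.59 points. This is the weight of any single subject, not an estimate of the effect.

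**The case against.** The strongest reply is that both points are translation. The SAP rewords the protocol throughout ('pass' for success, 'deficiency' for defect, 'test' for investigational). Its related list has three descending levels starting at 'definitely', just as the protocol's does. SAP section 9 presents the SAP as a more detailed account of the protocol's indicators and announces no change to the causality rule. 'Severe' for 'serious' fits the flowchart row and avoids a redundant table. Protocol 5.3.2 already defines SAE incidence, protocol 6.4 requires descriptive analysis of the safety indicators, and the table shells are in a separate document not available here. Follow-up ends 1 hour after the flush, and the only adverse event foreseen is a transient taste or odour disturbance, so few events may be at issue.

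Much of this stands. A reader might infer that the sponsor narrowed the definition of device-related events, or that SAEs will not be summarised. The documents support neither. Nothing signals an intended change of rule, and with mixed wording and unseen shells a missing SAE table is not shown. All adverse events are listed, and deaths have their own summary.

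What does not fall away is the wording. A translation slip in an analysis rule still has to be corrected, because the SAP offers no mapping and 'probably' is itself a protocol grade with a different meaning. A listing is also not the incidence by group that protocol 5.3.2 defines.

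**Conclusion.** The causality labels are wrong as written: SAP 6.4 and protocol 12.1.3 give different lists, and one SAP label is not on the scale. Whether events would be lost depends on the reading: the 'possibly related' grade drops out on the literal one, and nothing drops out on the translation one. The serious-event wording is ambiguous, and the documents do not show more than that.

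The severity is minor. The primary non-inferiority result is untouched, events left out of the device-related table remain in the all-TEAE table or the listing, and SAP 6.1 makes between-group comparisons other than the primary one exploratory. The conclusion assumes that causality is recorded on the protocol's five grades. The shells may already resolve both parts, in which case only the SAP text needs correcting.

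**What to change.** In the SAP:

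- **(a)** In 6.4, use the three labels of protocol 12.1.3 word for word: definitely related, probably related and possibly related.
- **(b)** In 6.4, state that SAE incidence by group is summarised on the SS as protocol 5.3.2 defines it: subjects with an SAE under protocol 12.3, divided by total subjects. Show treatment-emergent SAEs as a sub-row. SAEs in subjects who were never randomized appear in the listing only.
- **(c)** Use 'severe' only for the grade and 'serious' only for SAEs. This includes the adverse-event row of Table 3.1 and the repeated-event rule in 6.4, which should say 'most severe' if the grade is meant.

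The cost is wording and at most one table, which the shells may already contain. Compared with the literal reading, the reported device-related rate may be slightly higher. Compared with the translation reading, it does not change.

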6.5 Other indicators

The number, frequency and proportion of all device deficiencies, device deficiencies leading to adverse events, and device deficiencies leading to serious adverse events occurring during the study period in each group are tabulated and summarized based on SS. All device deficiencies during the study period are detailed in the list.

7. DATA PROCESSING AND CONVERSION

7.1 Processing of missing data regarding primary effectiveness

The primary effectiveness indicators are not filled.

7.2 Missing of severity of adverse events

The severity of adverse events prior to flush syringe treatment is missing and is filled using "moderate". Missing of severity of adverse events occurring after the start of flush syringe treatment is filled using "severe" and these filled-in values are used for summary of occurrence rate only and are presented as original values in the final list.

8. INTERIM ANALYSIS

There will be no interim analysis in this trial.

9. REMARKS ON THIS PLAN

This Statistical Analysis Plan (SAP) provides a more technical and detailed description of the effectiveness and safety indicators than those in the study protocol (version v1.0, date <May 31, 2022>), and proposes specific statistical analysis methods for the relevant evaluation indicators, taking into account the numerical characteristics of the indicators in the study protocol, and in the context of the specific requirements of this study. Tables, graphs, and lists related to this plan will be provided in a separate, stand-alone document.

